4.1.2. General Considerations for Analyses During Maintenance Period

Maintenance Period starts at the first injection of study intervention at Week 16 and ends on the date of Week 68 or the ETV (between Weeks 16 and 68) unless specified otherwise.

For the efficacy and health outcome analyses, baseline is defined as the last available value before the first injection in the Induction Period and, in most cases, will be the value recorded at Baseline Visit (Visit 2, Week 0).

Unless otherwise specified, efficacy and health outcome variables at Week 16 prior to entering the Maintenance Period will be presented for the visit-wise reports for the Maintenance Period.

Unless specified otherwise, for the safety analyses during the Maintenance Period, baseline is defined as the last available value before the first injection in the Maintenance Period. In most cases, this will be the measure recorded at Week 16. For TEAEs, baseline is the events ongoing just prior to the first injection of the study drug injection at Week 16.

For participants in the MPP and MSP who met escape criteria (EASI-50 non-response) and escaped to lebrikizumab 250 mg Q2W at Weeks 20, 24, 28, 32, 36, 40, 44, 48, 52, 56, 60 and 64, only data in the Maintenance Blinded Period (up to the time of escape) will be included in both efficacy and safety analyses.

4.1.2.1. Maintenance Primary and Secondary Population

The number and percentage of participants achieving or maintaining categorical efficacy and health outcome responses will be summarized by treatment group for all scheduled visits, including Week 68.

Each continuous efficacy and health outcome measure score and the change from baseline (or percentage improvement) will be summarized by treatment group at all scheduled visits during the Maintenance Period, including Week 68 using descriptive statistics (n, mean, SD, median, minimum, and maximum). No inferential statistics will be provided for these populations.

For the MPP, the KM product limit method will be used to estimate the survival for time to event analyses (e.g., time to loss of IGA score of 0 or 1, or loss of EASI-50). A KM plot of the time to event by treatment group may be provided.

4.1.2.2. Maintenance Escape Population

For the Maintenance W16 Escape Population, the number and percentage of participants achieving or maintaining selected categorical efficacy and health outcome responses will be summarized by treatment group for all scheduled visits, including Week 68. Selected continuous secondary efficacy and health outcome measures score and the change from baseline (or percentage improvement) will be summarized by treatment group at all scheduled visits during the Maintenance Period, including Week 68 using descriptive statistics (n, mean, SD, median, minimum, and maximum). No inferential statistics will be provided for this population.

For the Maintenance W20-64 Escape Population who were treated with lebrikizumab 250 mg Q2W following loss of response (EASI-50 non-response), the number and percentage of participants regaining EASI-50 response or achieving EASI-75 will be summarized every 4 weeks after lebrikizumab 250 mg Q2W treatment. No inferential statistics will be provided for this population.

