**Table 2. Maintenance Period Dosing Schedule by Treatment Group**

Treatment Assignment in Induction Period (Blinded)	Treatment Assignment in Maintenance Period	Weeks 16, 20, 24, 28, 32, 36, 40, 44, 48, 52, 56, 60, and 64	Weeks 18, 22, 26, 30, 34, 38, 42, 46, 50, 54, 58, 62, and 66
Lebrikizumab 250 mg Q2W	Lebrikizumab 250 mg Q2W	1 active injection	1 active injection
	Lebrikizumab 250 mg Q4W	1 active injection	1 placebo injection
Lebrikizumab 250 mg Q4W	Lebrikizumab 250 mg Q4W	1 active injection	1 placebo injection
Placebo	Placebo	1 placebo injection	1 placebo injection

Abbreviations: SC = subcutaneous; Q2W = every 2 weeks; Q4W = every 4 weeks.

Notes: Information provided in this table may change throughout the study. Injections are given SC.

### Participants Entering Escape Arm at Week 16

Participants who achieve neither an IGA 0 or 1 nor an EASI-75 response (<EASI-75) at Week 16 will move to the Escape Arm.

Participants who require high-potency topical or systemic rescue treatment for AD during the Induction Period will be eligible for treatment in the Escape Arm. Participants receiving systemic rescue medication in the Induction Period will be required to washout for 5 half-lives prior to initiating treatment in the Escape Arm.

Participants who are eligible for the Escape Arm at Week 16 will receive blinded loading doses at Week 16 and 18, based on their prior treatment assignment, followed by 250 mg lebrikizumab Q2W through Week 68 in the Escape Arm in an open-label fashion. Participants not achieving an EASI-50 response at 2 consecutive visits in the Escape Arm after Week 32 of treatment will be terminated from the study.

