### **Participants Entering Escape Arm at Week 20, 24, 28, 32, 36, 40, 44, 48, 52, 56, 60, or 64**

Participants who do not maintain an acceptable response (have an EASI score <50% of baseline) at Week 20, 24, 28, 32, 36, 40, 44, 48, 52, 56, 60, or 64 in the Maintenance Period will be eligible for treatment in the Escape Arm and will receive 250 mg lebrikizumab Q2W through Week 68 in the Escape Arm in an open-label fashion. Participants not achieving an EASI-50 response at 2 consecutive visits after 8 weeks of treatment in the Escape Arm will be discontinued from the study.

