## 7.2. Participant Discontinuation/Withdrawal from the Study

A participant may withdraw from the study:

- at any time at his/her own request
- at the request of his/her designee (for example, parents or legal guardian)
- at the discretion of the investigator for safety, behavioral, compliance, or administrative reasons
- if the participant becomes pregnant during the study
- if enrollment in any other clinical study involving an IP or enrollment in any other type of medical research judged not to be scientifically or medically compatible with this study
- if the participant, for any reason, requires treatment with another therapeutic agent that has been demonstrated to be effective for treatment of the study indication, discontinuation from the study occurs prior to introduction of the new agent
- if a participant transitioned to the Escape Arm from Week 16 (use of rescue treatment in the Induction Phase or non-responder at Week 16) and does not achieve an EASI-50 response at 2 consecutive visits after Week 32
- if a participant is transitioned to the Escape Arm after Week 20 and does not achieve an EASI-50 response at 2 consecutive visits after 8 weeks of treatment

- if a participant requires long-term systemic treatment for symptoms of AD in the Maintenance Period (for example, non-responders), or
- if an investigator, site personnel performing assessments, or participant is unblinded.

Discontinuation is expected to be uncommon.

At the time of discontinuing from the study, if possible, an early discontinuation visit should be conducted, as shown in the SoA (Section 1.3). See the SoA (Section 1.3) for data to be collected at the time of study discontinuation and follow-up and for any further evaluations that need to be completed. The participant will be permanently discontinued both from the study intervention and from the study at that time.

If the participant withdraws consent for disclosure of future information, the sponsor may retain and continue to use any data collected before such a withdrawal of consent. If a participant withdraws from the study, he/she may request destruction of any samples taken and not tested, and the investigator must document this in the site study records.

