1.1.1.2.4. Maintenance Supportive Estimand for Continuous Endpoints (Hypothetical)

The maintenance supportive estimand for continuous endpoints only is a hypothetical estimand representing the clinical question of interest: what is the means for each treatment condition (i.e., Lebrikizumab 250 mg Q2W and Lebrikizumab 250 mg Q4W), in the target participant population, in means after 68 weeks if rescue medication was not available and all participants adhered to the treatment and did not transfer to escape arm?

The maintenance supportive estimand is described by the following attributes:

- A. Population: MPP as described in Section 3
- B. Endpoint: apply to all continuous endpoints for the Maintenance Period
- C. How to account for ICEs
 - a. For participants who require any use of rescue medication, discontinue treatment after Week 16, or transfer to escape arm, a hypothetical strategy will be used to estimate what the means for each treatment condition would have been if rescue medication was not available and all participants adhered to the treatment and did not transfer to escape arm. Therefore, hypothetical strategy is used for these types of ICEs.
- D. Population-level summary: means for each treatment condition

Details on how missing data including those as a result of intercurrent events will be handled can be found in Section 4.1.6.2. Detailed analyses relative to estimands including analysis type, method and imputation, population, time point, and treatment comparisons for efficacy and health outcome analyses can be found in [Appendix 2](#).

The table below summarizes the analytical strategies that will be conducted on the intercurrent events for the four maintenance estimands. Intercurrent events and missing data will be summarized by treatment group for the Induction Period on the ITT population, and for the Maintenance Blinded Period on the MPP, respectively.

Description of Primary and Supportive Estimands for Maintenance Period

Maintenance Estimand	Analysis Strategy for Intercurrent Events				Transfer to Escape Arm	Missing Data Imputation Method		
	Rescue Medication		Treatment Discontinuation					
	Topical rescue medication	Systemic rescue medication	Due to lack of efficacy	Due to any other reasons				
Maintenance Primary Estimand (Hybrid)	Hypothetical: Set to missing	Composite: Set to baseline	Composite: Set to baseline	Hypothetical: Set to missing	Composite: Set to baseline	Primary analysis: MCMC-MI		

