Intent-to-Treat (ITT)	All randomized participants, even if the participant does not take the assigned treatment, does not receive the correct treatment, or otherwise does not follow the protocol. Participants will be analyzed according to the treatment group to which they were assigned. Unless otherwise specified, efficacy and health outcome analyses for the Induction Period will be conducted on this population.
Safety Population	All randomized participants who received at least 1 dose of study intervention during the Induction Period. Safety analyses for the Induction Period will be conducted on this population.
Per-Protocol Set (PPS)	All ITT participants who do not have a subset of important protocol deviations that impact the primary efficacy endpoint. Important protocol deviations are defined in a separate document referred to as "The KGAL Trial Issues Management Plan." Primary efficacy analysis for IGA score of 0 or 1 and EASI-75 will be repeated using the PPS.
Maintenance Primary Population (MPP)	All participants who were randomized to lebrikizumab 250 mg Q2W or lebrikizumab 250 mg Q4W at baseline visit (Visit 2, Week 0) and met the response criteria (that is, participants who achieved an IGA score of 0 or 1 and/or EASI-75 at Week 16) and received at least 1 dose of study intervention during the Maintenance Period. Participants will be analyzed according to the treatment to which they were assigned. Only information prior to entering the Escape Arm will be presented. Efficacy, health outcome, and safety analyses for the Maintenance Period will be conducted primarily on the MPP.
Maintenance Secondary Population (MSP)	Participants who were randomized to placebo at baseline visit (Visit 2, Week 0) and continued placebo (that is, participants who achieved an IGA score of 0 or 1 and/or EASI-75 at Week 16) and received at least 1 dose of study intervention during the Maintenance Period. Only information prior to entering the Escape Arm will be presented. Selective efficacy analyses for the Maintenance Period will be conducted on the MSP.

Maintenance W16 Escape Population	Participants who moved to the Escape Arm at Week 16 (either due to not meeting IGA and EASI criteria, or used rescue therapy during the Induction Period), and received at least one dose of study intervention during the Maintenance Period. Selective efficacy analyses for the Maintenance Period will be conducted on the Maintenance W16 Escape Population.

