Maintenance W20-64 Escape Population	Participants in MPP or MSP who escaped to lebrikizumab 250 mg Q2W due to EASI-50 non-response at Weeks 20, 24, 28, 32, 36, 40, 44, 48, 52, 56, 60 or 64. Selective efficacy analyses for the Maintenance Period will be conducted on the Maintenance W20-64 Escape Population to assess whether these participants re-gain EASI-50 response or achieve a higher level of response (for example, EASI-75) following re-treatment.
All Maintenance Population	Participants who entered the Maintenance Period and received at least one dose of study intervention during the Maintenance Period.
All Lebrikizumab Safety Population	All randomized participants who received at least 1 dose of lebrikizumab treatment during the Combined Induction and Maintenance Periods including participants who were randomized to placebo at baseline visit (Visit 2, Week 0) and moved to the Escape Arm at Week 16 or later visits in the Maintenance Period. Safety analyses for the Combined Induction and Maintenance Periods will be conducted on the All lebrikizumab Safety Population. Selective safety analyses for the Combined Induction and Maintenance Periods plus the Follow-Up Period will be conducted on the All Lebrikizumab Safety Population.
Pharmacokinetic Analysis	All participants who received at least 1 dose of lebrikizumab and have at least 1 evaluable PK sample.

Abbreviations: EASI-75 = $\geq 75\%$ reduction from baseline in Eczema Area and Severity Index IGA = Investigator's Global Assessment; Q2W = every 2 weeks; Q4W = every 4 weeks; W = Week.

Treatment Groups and Comparisons for Each Study Period and Analysis Population

Study Period	Analysis Population	Treatment Groups	Abbreviation	Inferential Comparisons When Applicable
Induction Period	ITT; Safety; PPS	Placebo; Lebrikizumab 250 mg Q4W; Lebrikizumab 250 mg Q2W; Total	PBO; LEB250Q4W; LEB250Q2W; Total	LEB250Q4W vs PBO; LEB250Q2W vs PBO
Maintenance Blinded Period	MPP	Lebrikizumab 250 mg Q4W_Res/ Lebrikizumab 250 mg Q4W; Lebrikizumab 250 mg Q2W_Res/ Lebrikizumab 250 mg Q4W; Lebrikizumab 250 mg Q2W_Res/ Lebrikizumab 250 mg Q2W; Total	LEB250Q4W_Res/ LEB250Q4W; LEB250Q2W_Res/ LEB250Q4W; LEB250Q2W_Res/ LEB250Q2W; Total	No Between-Group or Overall Comparisons
Maintenance Blinded Period	MSP	Placebo_Res/Placebo	PBO_Res/PBO	No Between-Group or Overall Comparisons

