4.1.6.2.1. Maintenance Period MCMC-MI

The MCMC-MI will be used to handle missing data relative to the maintenance primary estimand (Hybrid) and the maintenance supportive estimand (Hybrid) for both binary and continuous endpoints. Imputation will be conducted within each treatment group independently so the pattern of missing observations in one treatment group cannot influence missing value imputation in another. The SAS PROC MI with MCMC option will be used to conduct the MCMC-MI. The imputation model will include the relevant baseline and post-baseline.

For each imputation process, 25 datasets with imputations will be calculated. The initial seed values are given in the table below. Each complete data set will be analyzed with the specified

analysis. The results from these analyses will be combined into a single inference using SAS PROC MIANALYZE.

The imputation and analysis will be conducted on the MPP only.

The derivation of binary responses related to EASI, IGA and Itch NRS for the Maintenance Period will follow the derivation for the Induction Period. For the derivation of percentage change from baseline in EASI, the imputed values will be used directly to compare with baseline EASI.

Seed Values for MCMC-MI for Maintenance Period

Analysis	Seed values
	Lebrikizumab 250 mg Q2W
	Lebrikizumab 250 mg Q4W
IGA	12345
EASI	12346
Itch NRS	12347

Abbreviations: EASI = Eczema Area and Severity Index score; IGA = Investigator's Global Assessment for AD; MCMC-MI = Markov chain Monte Carlo multiple imputation; NRS = Numeric Rating Scale; Q2W = every 2 weeks; Q4W=every 4 weeks.

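### Late Escape Arm means, and percentages if based on observed cases, describe only participants who passed the EASI-50 withdrawal rule; the SAP should set a denominator and a rule for those withdrawn

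*SAP*

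**What the plan says.** **Withdrawal rule.** Protocol 6.1 ends participation for Week 16 entrants who miss EASI-50 "at 2 consecutive visits in the Escape Arm after Week 32 of treatment". For later entrants, those without an EASI-50 response "at 2 consecutive visits after 8 weeks of treatment in the Escape Arm will be discontinued from the study". Section 7.2 repeats both rules as reasons for leaving the study, the first as a participant who "does not achieve an EASI-50 response at 2 consecutive visits after Week 32". It adds that treatment and study participation stop together.

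**Escape populations.** SAP Section 3 defines them by entry: "Participants who moved to the Escape Arm at Week 16", and "Participants in MPP or MSP who escaped to lebrikizumab 250 mg Q2W due to EASI-50 non-response". Section 4.1.2.2 plans numbers and percentages, plus descriptive statistics for selected continuous measures in the Week 16 group, without inferential tests. For the later group, "the number and percentage of participants regaining EASI-50 response or achieving EASI-75 will be summarized every 4 weeks" after the start of Q2W treatment.

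**Missing data.**
- All four Maintenance estimands (SAP 1.1.1.2) have the Maintenance Primary Population (MPP) as their population.
- For multiple imputation, SAP 4.1.6.2.1 states: "The imputation and analysis will be conducted on the MPP only".
- The Maintenance NRI and LOCF rules (4.1.6.2.2 and 4.1.6.2.3) treat transfer to escape as an intercurrent event.
- The escape rows of Appendix 2 give no estimand and name plain descriptive statistics. Other rows specify NRI, LOCF or observed data.
- Appendix 1 makes EASI-50, EASI-75 and EASI-90 missing when the visit score is missing.

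**Attrition reporting.** Intercurrent events and missing data are summarised for the Induction Period "on the ITT population, and for the Maintenance Blinded Period on the MPP, respectively". SAP 4.2 tabulates Maintenance Period discontinuations by reason for the MPP and the Maintenance Secondary Population only.

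**The concern.** The protocol removes participants because of the outcome being summarised. Once they leave, they contribute no EASI score, and no SAP rule says how they count at later visits. A by-visit mean is then taken over those who remain, all of whom have passed the EASI-50 test. A percentage on the same basis has the same selection. Such a summary can rise from one visit to the next with nobody improving.

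The stake is descriptive but not trivial. SAP Section 3 says the later-escape analysis is meant to assess whether participants regain EASI-50, and failing EASI-50 is the withdrawal trigger. The Week 52 lock supports the initial Japanese submission, and the Week 16 escape group may be more than half the trial.

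**Working it through.** **The plan's own figures.** The plan gives no figure for the escape summaries. Its power claim reproduces by exact enumeration of the Fisher test (IGA 0/1: 97.9% for Q2W, 82.5% for Q4W) and does not bear on this point.

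**When the effect starts.** I read Week 32 as a study week, as Protocol 7.2 words it. The first two visits after it are Weeks 36 and 40, so withdrawals first change the Week 44 summary. For later entrants, visits strictly after 8 weeks are 12 and 16 weeks, and the effect starts at 20 weeks. If the 8-week visit counts, the pair is 8 and 12 and the effect starts at 16 weeks. Earlier visits are untouched.

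**How many participants.** The inputs are the arm sizes and EASI-75 planning rates in SAP Section 5 (58%, 53%, 20%). Expected Week 16 non-responders are 120 × 0.42 + 80 × 0.47 + 80 × 0.80 = 50.4 + 37.6 + 64 = 152 of 280. This is approximate: it ignores rescue users, dropouts and any IGA 0/1 responder without EASI-75.

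**Formula.** With N entrants, W withdrawn and x responders still in study, the fixed-denominator rate is x/N and the observed-case rate is x/(N − W). So the observed-case rate equals the fixed rate divided by the share still in study.

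**Illustration, Week 16 entrants at Week 52.** All inputs are assumed. Each person's EASI improvement is normal with the mean and SD shown, visit noise has SD 12, values are capped at 100, and there is no change over time. Exit follows two consecutive visits below 50%. There were 400,000 simulated participants per row.

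| Mean / SD | Still in study | True EASI-75 | Observed cases | Fixed denominator |
|---|---|---|---|---|
| 80 / 15 | 96% | 60.3% | 62.5% | 60.1% |
| 70 / 20 | 82% | 41.5% | 49.9% | 41.1% |
| 70 / 30 | 74% | 43.9% | 58.9% | 43.6% |

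The overstatement is 62.5 − 60.3 = 2.2, 49.9 − 41.5 = 8.4 and 58.9 − 43.9 = 15.0 points. As a check on the formula, row 3 gives 43.6 / 0.74 = 58.9.

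**Mean EASI improvement (%), same sets.**

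| Mean / SD | True | Observed cases | LOCF | Withdrawn set to baseline |
|---|---|---|---|---|
| 80 / 15 | 78.5 | 79.6 | 78.0 | 76.5 |
| 70 / 20 | 68.9 | 74.5 | 67.7 | 61.4 |
| 70 / 30 | 66.9 | 78.6 | 65.8 | 58.2 |

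LOCF errs by −0.5, −1.2 and −1.1 points. Setting withdrawn participants to baseline errs by −2.0, −7.5 and −8.7, against +1.1, +5.6 and +11.7 for observed cases. It is further from the truth than observed cases in the first two rows.

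**Later escapers at 20 weeks, same model.** Figures are true / observed cases / fixed denominator.

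| Mean / SD | EASI-50 (%) | EASI-75 (%) |
|---|---|---|
| 70 / 20 | 80.4 / 87.4 / 77.3 | 41.6 / 46.8 / 41.4 |
| 50 / 20 | 50.1 / 71.2 / 44.1 | 14.1 / 22.5 / 13.9 |
| 50 / 30 | 49.9 / 78.2 / 45.7 | 22.0 / 37.4 / 21.9 |

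From the EASI-50 column, the share still in study is 77.3/87.4 = 88%, 44.1/71.2 = 62% and 45.7/78.2 = 58%. The larger gaps therefore need heavy withdrawal.

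**The case against.** **The SAP never says that percentages use observed cases.** A reader might infer that they will be inflated. The documents do not support that. Section 3 fixes the populations by entry, so all entrants is a natural denominator, and Appendix 2 labels observed-data analyses elsewhere but not in the escape rows. The table, figure and listing specifications are a separate document, which I have not seen, and may settle it. This objection stands for the percentages. It does not reach the means, which have no score to use for someone who has left. Nor does it say whether a missing response counts as a failure, since Appendix 1 leaves it missing.

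**Attrition is partly visible.** Responder counts are shown beside percentages, SAP 4.2 reports the size of each analysis population, continuous tables give n, and discontinuations are listed with reasons. For Week 16 entrants a careful reader could rebuild the fixed-denominator rate. That is harder for later escapers, because anyone escaping after Week 48 cannot reach 20 weeks by Week 68 (48 + 20 = 68), and that truncation mixes with withdrawal.

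**The effect may be small.** Protocol 7.2, the section that lists both EASI-50 rules, expects discontinuation to be uncommon. High-potency TCS is allowed in the Escape Arm and is not in the model. Both points stand.

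**The tables are uncontrolled and open-label after Week 20.** They cannot establish benefit on any denominator. That is right, and it limits the weight of this point.

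**Conclusion.** The gap is real and worth closing before the Week 52 lock. On the text as written, late continuous escape summaries are restricted to participants who passed the EASI-50 test. The percentages are restricted in the same way only if observed cases are the denominator.

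The direction follows from the withdrawal rule; the size does not. For EASI-75 at Week 52 it is about +2 points with 4% withdrawn. A reader might take the +8 and +15 point figures as forecasts, but they are illustrations that need 18% and 26% withdrawn, and the documents give no withdrawal fraction. All sizes rest on assumed distributions, a flat course over time and no other dropout.

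A reader might also infer that the trial's main conclusions are at risk. They are not. The co-primary and major secondary tests concern the Induction Period, MPP results use only data before escape, and the escape tables carry no comparisons.

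**What to change.** In SAP 4.1.2.2 and the escape rows of Appendix 2:

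- **Percentages.** Use a fixed denominator: all Week 16 escape entrants; for Weeks 20 to 64, all escapers whose entry visit allows that follow-up by Week 68 (escape by Week 48 for the 20-week row). Count participants withdrawn under the EASI-50 rule or for lack of efficacy as non-responders at later visits. This extends the SAP's own principle for the MPP, where discontinuation for lack of efficacy is treatment failure. State how departures for other reasons are counted.
- **Alongside.** Show the observed-case result, with the number still in study and the cumulative number withdrawn under the rule at each visit.
- **Continuous scores.** Do not set withdrawn participants to baseline. Add an LOCF summary that carries forward the last score in the Escape Arm, beside the observed-case means. LOCF is already the SAP's supportive method for continuous Maintenance endpoints.

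The SAP should state the downside. The fixed-denominator EASI-50 rate is somewhat conservative, because some withdrawn participants might have responded later (77.3% against a true 80.4%, and 44.1% against 50.1%, above). The EASI-75 rate is close to neutral. The cost is SAP text and table programming, with no added visits, procedures or participants. If the table specifications already set this denominator, the percentage part needs one sentence in the SAP.
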